**Statistics continued:**

**Efficacy Analysis:** The primary efficacy endpoint will be analyzed using a 2-sided Fisher Exact test and a logistic regression model to control for the stratification factor (time since COVID-19 diagnosis); the method of Firth will be used to predict outcomes. A 2-sided Wilcoxon rank sum test will be used to compare the distributions of scores on the 8-point WHO Ordinal Clinical Scale for the 2 treatment groups. Continuous endpoints will be evaluated using a mixed model repeated measures analysis using a compound symmetry error structure. Time to event outcomes (e.g., extubation, hospital discharge, death) will be displayed using a Kaplan-Meier life table and treatment distributions compared using a stratified log-rank test and Cox proportional hazards model to control for time since diagnosis and treatment including the interaction term. A Greenwood test will be performed using the Day 28 estimates from the Kaplan-Meier lifetable.

**Safety Analysis:** Safety measures including adverse events, clinical laboratory tests, vital signs, physical examinations, and concomitant medication usage will be summarized descriptively by treatment group.

When appropriate, summary statistics will be provided (number of non-missing values, mean, median, standard deviation, minimum, and maximum for continuous variables and number and percentage of patients for categorical variables) by treatment group for all measures, including demographic and baseline assessments, safety, and efficacy endpoints. Baseline for all safety and efficacy endpoints is defined as the last observations before administration of study drug. No imputation will be used for missing data.

**Interim Analyses:** A group sequential design will be conducted with 4 pre-planned interim analyses after 30, 60, and 90 subjects complete the Day 7 evaluation and 150 subjects complete the Day 28 evaluation. At each interim, the DSMB will evaluate an independently conducted analysis in order to assess safety and futility.

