## 7 STUDY OBJECTIVES

The overall objective is to evaluate the efficacy, tolerability, and safety of a single dose of RBT-9 versus placebo on the progression of COVID-19 infection in non-critically ill adults who are at high risk due to age and/or comorbid conditions.

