## **9.2 Exclusion Criteria**

Subjects will be ineligible for study participation if they meet any of the following criteria:

1. Anticipated need for ICU care and/or ventilatory support (invasive or non-invasive) within 24 hours.
2. Evidence of acute cardiac injury, as determined by the Investigator at the time of Screening. This may be based upon clinical signs and symptoms, ECG findings, or elevated troponin I.
3. Evidence of acute kidney injury not due to pre-renal azotemia or urinary tract obstruction at the time of Screening.
4. Oxygen saturation <90% on supplemental oxygen with a nasal cannula, including high-flow oxygen.
5. Requires non-invasive ventilation at the time of Screening.
6. Requires dialysis at the time of Screening.
7. Has received or is receiving anti-IL-6 therapies (eg, Tocilizumab, Sarilumab, Silituximab, etc) for the treatment of COVID-19; subjects receiving anti-IL-6 therapies for underlying medical conditions that are unrelated to COVID-19 are not excluded from eligibility.
8. Pregnant or lactating.
9. History of photosensitivity or active skin disease that, in the opinion of the Investigator, could be worsened by RBT-9.
10. Known hypersensitivity or previous anaphylaxis to RBT-9 (stannous protoporphyrin) or any tin-based product.
11. Treatment with an investigational drug or participation in an interventional trial within 30 days prior to treatment with study drug.
12. Has received COVID-19 vaccination.

13. Has received anti-SARS-CoV-2 antibody therapy.
14. Inability to comply with the requirements of the study protocol.

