#### **11.1 Endpoints**

The following efficacy endpoints are defined for the study.

Primary Endpoint: Percentage of subjects in each treatment group in categories 4 through 8 of the 8-point WHO Ordinal Clinical Scale through Day 28.

Secondary Endpoints:

- Time to first occurrence of either death from any cause or new/worsened organ dysfunction through Day 28, defined as at least one of the following:
  - Respiratory decompensation
  - New or worsening congestive heart failure
  - Requirement of vasopressor therapy and/or inotropic or mechanical circulatory support
  - Ventricular tachycardia or fibrillation lasting at least 30 seconds and/or associated with hemodynamic instability or pulseless electrical activity, or resuscitated cardiac arrest

- Initiation of renal replacement therapy.
- Percentage of subjects who are alive at Day 28.
- Among subjects who begin oxygen therapy, mean change from initiation to last day on oxygen or Day 28 (whichever happens first) in SpO2/FiO2 ratio.
- Percentage of subjects with fever through Day 28.
- Percentage of subjects who develop AKI, as determined by the Investigator, through Day 28.
- Percentage of subjects with new or worsening congestive HF through Day 28.
- Percentage of subjects with ventricular tachycardia or fibrillation lasting at least 30 seconds and/or associated with hemodynamic instability or pulseless electrical activity, or resuscitated cardiac arrest through Day 28.
- Percentage of subjects who remain hospitalized at Day 28.
- Length of hospitalization through Day 28.
- Number of oxygen-free days through Day 28.
- Percentage of subjects transferred to the ICU through Day 28.
- Number of days on mechanical ventilation through Day 28.
- Time to and duration of vasopressor or inotrope utilization through Day 28.
- Percentage of subjects who begin dialysis through Day 28.

Exploratory Endpoints:

- Duration of COVID-19 symptoms through Day 56

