## 11.2 Study Populations

The primary efficacy analysis will be conducted in the Intent-to-Treat population (all randomized subjects), and a secondary efficacy analysis will be conducted in the Per Protocol population (all randomized subjects who had no major protocol deviations). Safety analyses will be conducted in all subjects receiving any study drug.

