## 11.3 Data Analysis

The primary efficacy endpoint will be mapped to a binary endpoint (% categories 4-8) and then will be analyzed using a two-sided Fisher Exact test and using a logistic regression model to control for the stratification factors; the method of Firth will be used to predict outcomes. A two-sided Wilcoxon rank sum test will be used to compare the primary efficacy endpoint distributions for the two treatment groups. Continuous endpoints will be evaluated using a mixed model repeated measures (MMRM) analysis using a compound symmetry (CS) error structure. Time to event outcomes (eg, extubation, WHO progression, death) will be displayed using a Kaplan-Meier (KM) lifetable and treatment distributions compared using a stratified log-rank test and Cox proportional hazards model to control for time since COVID-19 diagnosis.

When appropriate, summary statistics will be provided (number of non-missing values, mean, median, standard deviation, minimum, and maximum for continuous variables and number and percentage of patients for categorical variables) by treatment group for all measures, including demographic and baseline assessments, safety, and efficacy endpoints. Baseline for all safety and efficacy endpoints is defined as the last observations before administration of study drug. No imputation will be used for missing data.

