#### **11.4 Analysis of Efficacy Endpoints**

The primary efficacy endpoint will be analyzed using a 2-sided Fisher Exact test and a logistic regression model to control for the stratification factors; the method of Firth will be used to predict outcomes. A 2-sided Wilcoxon rank sum test will be used to compare the distributions of scores on the 8-point WHO Ordinal Clinical Scale for the 2 treatment groups. Continuous endpoints will be evaluated using a mixed model repeated measures analysis using a compound symmetry error structure. Time to event outcomes (eg, extubation, hospital discharge, death) will be displayed using a Kaplan-Meier life table and treatment distributions compared using a stratified log-rank test and Cox proportional hazards model to control for time since diagnosis and treatment including then interaction term. A Greenwood test will be performed using the Day 28 estimates from the Kaplan-Meier lifetable.

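### Time to extubation is named for a between-arm survival comparison although subjects enter unintubated; neither available at-risk set gives a sound randomized comparison

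*Combined protocol and SAP*

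**What the plan says.** Extubation is the first example of a time-to-event outcome in three places.

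- Section 11.4: "Time to event outcomes (eg, extubation, hospital discharge, death) will be displayed using a Kaplan-Meier life table". The arms are then compared by stratified log-rank test and Cox model, with a Greenwood test on the Day 28 Kaplan-Meier estimates.
- Section 11.3: "Time to event outcomes (eg, extubation, WHO progression, death) will be displayed using a Kaplan-Meier (KM) lifetable". Log-rank and Cox are named again, without the Greenwood test.
- Synopsis, Statistics: "Time to event outcomes (e.g., extubation, hospital discharge, death) will be displayed using a Kaplan-Meier life table", with the Greenwood test.

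Section 7 gives the aim as to "evaluate the efficacy, tolerability, and safety of a single dose of RBT-9 versus placebo on the progression of COVID-19 infection in non-critically ill adults". Section 9.2 excludes subjects with "Anticipated need for ICU care and/or ventilatory support (invasive or non-invasive) within 24 hours" (criterion 1) and anyone who "Requires non-invasive ventilation at the time of Screening" (criterion 5). No criterion uses the word intubated, but together these leave no room for an intubated subject at entry.

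On analysis sets, section 11.2 says: "The primary efficacy analysis will be conducted in the Intent-to-Treat population (all randomized subjects"). The only other efficacy set is Per Protocol. Section 11.1 does not list time to extubation; its ventilation endpoint is the number of days on mechanical ventilation. That section can restrict a denominator when it means to: "Among subjects who begin oxygen therapy, mean change from initiation to last day on oxygen or Day 28". Nothing similar is said for extubation. No time origin, at-risk set or rule for never-intubated subjects is given.

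**The concern.** A survival analysis needs subjects who are at risk of the event from time zero. Here nobody is at risk of extubation at randomization. A subject becomes at risk only through a bad outcome that treatment may change. Take three courses, analysed from randomization:

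- A: never intubated, discharged on Day 4. No extubation event; censored.
- B: intubated on Day 6, extubated on Day 12. Event on Day 12.
- C: intubated on Day 6, still ventilated on Day 28. No event; censored.

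The best course (A) and the worst (C) both end without an event, and only the middle one (B) counts as a success. This is separate from the handling of deaths: it remains if nobody dies.

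At stake is a respiratory comparison that could look unfavourable because the drug prevented intubation. The Day 28 Greenwood test would carry the same problem, since it uses the same curves.

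**Working it through.** **Inputs.** From the documents: 84 placebo and 168 RBT-9 subjects (section 11.6). The plan gives no figure for extubation to reproduce. The power table that supplies the group sizes does reproduce with a pooled chi-square at two-sided 0.045: 84.9%, 85.6% and 84.6%, against the stated 84%, 85% and 84%. The documents give no intubation or extubation rates, so every rate below is an assumption.

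**Step 1. All randomized subjects, equal prognosis once intubated.** For each arm,

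P(extubated by Day 28) = P(intubated) x P(extubated | intubated).

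Assume intubation of 15% v 7.5% and a 50% chance of extubation in both arms:

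- Placebo: 0.15 x 0.50 = 7.5%.
- RBT-9: 0.075 x 0.50 = 3.75%.
- Approximate hazard ratio: ln(1 - 0.0375) / ln(1 - 0.075) = 0.49.

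With placebo intubation of 10-30%, extubation chance of 30-70% and intubation halved, the hazard ratio is 0.47-0.50. If intubation falls by a quarter instead, it is 0.73-0.75.

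**Step 2. All randomized subjects, prognosis depending on severity.** Let severity S be standard normal, with intubation when S exceeds a cut-off c set to give 15% on placebo. Let P(extubated | S) = logistic(1 - 2(S - c)) in both arms. About 50% of intubated placebo subjects are then extubated. Halve intubation in two ways:

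- Severity shifts evenly: 53% of intubated RBT-9 subjects are extubated; 0.075 x 0.53 = 4.0% of the arm.
- The milder half of intubations is prevented: 35% are extubated; 0.075 x 0.35 = about 2.7% of the arm.

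Against 7.5% on placebo the ratio is about 0.53 or 0.35. At placebo intubation of 10% or 20% it stays within about 0.34-0.54.

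**Step 3. Raw counts under 2:1 allocation.** Placebo: 84 x 0.075 = 6.3 extubations. RBT-9: 168 x 0.0375 = 6.3 (Step 1), 168 x 0.040 = 6.7 (even shift) or 168 x 0.027 = 4.5 (milder half). The proportion and hazard fall; the count need not.

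**Step 4. How often this would show.** This simulates 1,000 trials per scenario with an unstratified log-rank test and Cox model. Intubation is uniform over Days 2-14, time on ventilator is exponential with mean 8 days, 60% of intubated subjects can be extubated in either arm, and everyone without an event is censored at Day 28.

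| Placebo intubation | Effect on intubation | Extubated, placebo v RBT-9 | Median HR | HR < 1 | p < 0.05 against RBT-9 |
|---|---|---|---|---|---|
| 15% | halved | 8.1% v 4.1% | 0.49 | 90% | 26% |
| 30% | halved | 16.4% v 8.2% | 0.48 | 96% | 52% |
| 15% | none | 8.1% v 8.3% | 1.01 | 49% | 2.5% |

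The last row shows that the unfavourable hazard ratio comes from the benefit on intubation.

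**Step 5. Intubated subjects only.** Expected numbers are 84 x 0.15 = 12.6 and 168 x 0.075 = 12.6, about 13 per arm. Under Step 2 the extubated share is 50% v 53% (even shift) or 50% v 35% (milder half prevented). With no direct drug effect on extubation, selection alone moves the difference from 3 points in favour of RBT-9 to 15 points against it.

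**The case against.** The strongest case on the other side is about weight. Extubation appears only as an example in a general methods sentence, and the examples vary: section 11.3 has WHO progression where 11.4 has hospital discharge. It is in neither the objectives nor the endpoint list, and has no bearing on the primary test, the interim analyses or the sample size. The opening of section 11 leaves data handling to a separate statistical analysis plan. Any odd extubation result would sit beside ventilator days, ICU transfer, survival and the organ-dysfunction composite, which would show a real benefit. All of this stands, and it limits the importance of the point.

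It does not remove the point. A separate plan would still have to choose between all randomized subjects and intubated subjects, and neither choice gives a sound randomized comparison. An outcome named three times together with its tests is likely to be analysed.

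A reader might go further in three ways that the documents do not support.

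- That the plan fixes an all-randomized analysis of extubation, so the result will be in the wrong direction. Section 11.2 assigns the Intent-to-Treat set to the primary efficacy analysis only. Its use for extubation is an inference from the lack of any other efficacy set except Per Protocol, which has the same defect.
- That the better arm would have fewer extubation events. Under 2:1 allocation the counts can be equal, or slightly higher on RBT-9 (Step 3).
- That an intubated-only analysis would be biased against the drug. Step 5 gives either sign, depending on which intubations are prevented.

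**Conclusion.** The concern holds as a defect in a named but unlisted analysis. Because intubation can occur only after randomization, time to extubation has no at-risk set that supports a valid between-arm test. In all randomized subjects, preventing intubation lowers the cumulative proportion and hazard of extubation; the direction follows from the definition when prognosis once intubated is similar in the two arms. The size depends on assumed rates: about 7.5% v 2.7-4.0% for 15% v 7.5% intubation, a ratio of about 0.35-0.53. In intubated subjects only, about 13 per arm, the bias has no established sign or size.

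The primary analysis and the sample size are unaffected. A reader might infer that the trial's main conclusion is at risk, or that it lacks a usable respiratory time-to-event endpoint. Neither follows: section 11.1 already lists time to death or new/worsened organ dysfunction, including respiratory decompensation.

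**What to change.** Delete extubation from the tested time-to-event outcomes in sections 11.3 and 11.4 and in the synopsis. Report extubation among intubated subjects as a listing or descriptive table, with no between-arm test.

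If the sponsor wants a formal ventilation comparison, use one defined for all randomized subjects from randomization, such as time to first intubation or death through Day 28. List it in section 11.1 and analyse it with the stratified log-rank test and Cox model already planned. This is optional; otherwise rely on the listed time to death or new/worsened organ dysfunction.

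The cost is wording in three places, plus one endpoint line if the option is taken. The optional endpoint needs dates of first intubation and death. The listed number of days on mechanical ventilation already calls for ventilation timing, so little or no new data collection should be needed. The downside is that extubation timing gets no formal test, which about 13 intubated subjects per arm could not support.

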### **9.3 Study Design**

This is a Phase 2, randomized, placebo-controlled, multicenter study that will evaluate the efficacy, tolerability, and safety of a single dose of RBT-9 on the progression of COVID-19 infection in non-critically ill adults who are at high risk due to age and/or comorbid conditions. Subjects with documented SARS-CoV-2 infection who are at high risk for disease progression, as defined in the inclusion criteria (see [Section 9.1](#)), and require observation and/or treatment in a hospital will be screened for entry into the study. Eligible subjects will be stratified by time since COVID-19 diagnosis (<48 hours,  $\geq$ 48 hours) and randomly assigned in a 2:1 ratio to receive a single intravenous infusion of 90 mg RBT-9 or placebo (normal saline). No more than 24 hours can elapse between Screening and Dosing of RBT-9.

All subjects will be assessed through Day 56. All subjects, regardless of hospitalization status, will be assessed on Days 7, 14, 21, and 28, according to the Event Schedule (see [Section 5.1](#)). Assessments will include severity of COVID-19 measured by the 8-point WHO Ordinal Clinical Scale, physical examination, vital signs, clinical laboratory evaluations, concomitant medications, and adverse events. For subjects who have been discharged from the hospital, visits on Days 7, 14, and 21 will be conducted virtually (eg, by telephone or video contact). The Day 28 visit should be conducted in person, but may be conducted virtually, as well. Subjects will also be assessed at safety follow-up visits, which will be conducted virtually (eg, by telephone or video contact) on Days 42 and 56.

An independent data and safety monitoring board (DSMB) will actively monitor interim data to make recommendations regarding study conduct/continuation. The DSMB will meet once the first 30 subjects complete the Day 7 assessment to perform the first interim analysis of the safety data. Enrollment of 30 additional subjects will proceed if the safety profile of RBT-9 is deemed acceptable (as determined by the DSMB). Two additional DSMB interim analyses will be performed once 60 and 90 subjects complete the Day 7 evaluation. The last DSMB interim analysis will be performed once 150 subjects complete the Day 28 evaluation; sample size re-estimation will also be performed to allow a sample size increase to 252 subjects based on pre-defined conditional power rules.

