#### **11.6 Sample Size Calculations**

The following table summarizes the RBT-9 advantages (15-18%) that can be detected with 84-85% power and 252 subjects for a 2-sided hypothesis test with 5% overall Type 1 error with 2-sided 4.5% Type 1 error remaining at the final analysis; this alpha spend accounts for the preplanned interim analyses.

Two group  $\chi^2$  test: Null hypothesis is Equal Failure %s (odds ratio = 1)

	84-85% Power			Two-sided p=0.045		
	1	2	3	1	2	3
Test significance level, $\alpha$	0.045	0.045	0.045	0.045	0.045	0.045
1 or 2-sided test?	2	2	2	2	2	2
Placebo Failure %, $\pi_1$	25%	32%	38%	25%	32%	38%
RBT Failure %, $\pi_2$	10%	15%	20%	14.6%	20.4%	25.7%
Odds ratio, $\pi_2(1-\pi_1)/[\pi_1(1-\pi_2)]$	0.333	0.375	0.408	0.513	0.545	0.564
Power (%)	84	85	84	NA	NA	NA
Placebo sample size, n1	84	84	84	84	84	84
RBT sample size, n2	168	168	168	168	168	168
Ratio: n2 / n1	2	2	2	2	2	2
N = n1 + n2	252	252	252	252	252	252

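### Section 11.4 and the synopsis put a treatment-by-diagnosis-time interaction in the Cox model, Section 11.3 names none, and the plan does not define which hazard ratio is reported

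*Combined protocol and SAP*

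**What the plan says.** The randomization has one stratification factor with two levels, under 48 hours and 48 hours or more since diagnosis. Section 9.3: "Eligible subjects will be stratified by time since COVID-19 diagnosis". Allocation is 2:1.

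Three places describe the Cox analysis of time-to-event outcomes:

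- Section 11.4: a Cox model to "control for time since diagnosis and treatment including then interaction term".
- Synopsis (Section 4, Statistics continued): "Cox proportional hazards model to control for time since diagnosis and treatment including the interaction term".
- Section 11.3: "stratified log-rank test and Cox proportional hazards model to control for time since COVID-19 diagnosis", with no interaction mentioned.

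All three pair the Cox model with a stratified log-rank test. The example outcomes differ slightly, but extubation and death appear in each, so the three passages cover the same analyses. The first-listed secondary endpoint in Section 11.1, time to death or new or worsened organ dysfunction through Day 28, falls under them. The opening of Section 11 leaves full statistical detail to a separate analysis plan.

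**The concern.** Sections 11.4 and 4 name only two terms, so the interaction is treatment by diagnosis-time stratum. Placing it inside the model used to compare treatments changes what the treatment coefficient means. Without it, the coefficient is one log hazard ratio for the trial. With it, the meaning depends on how the stratum is coded, and the plan does not say.

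The stratified log-rank test gives a p-value but no effect size. The Cox model is the only method named that yields a hazard ratio, yet the plan does not say which version supplies the figure. A hazard ratio that applies to one stratum, printed beside a log-rank p-value for the whole trial, could disagree with it and be misread as the overall effect. Because treatment assignment is open-label (Sections 9.5, 9.6 and 10.5), an unstated choice of model, coding and reference level is better closed in advance.

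**Working it through.** **The plan's own figures.** The only power figures are in Section 11.6, for a chi-square test on the binary primary endpoint with 84 and 168 subjects and "2-sided 4.5% Type 1 error remaining at the final analysis". With pooled variance under the null and unpooled variance under the alternative, 25% v 10%, 32% v 15% and 38% v 20% give 84.9%, 85.6% and 84.6%, against 84%, 85% and 84% stated. They reproduce, but they say nothing about the Cox model. The documents give no event count, hazard ratio, stratum share or power for any time-to-event outcome, so what follows is illustration.

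**What the coefficient is.** Let b1 and b2 be the log hazard ratios in the two strata.

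- No interaction: one coefficient b, a precision-weighted average of b1 and b2.
- Interaction, 0/1 coding: the treatment coefficient is b1 or b2, according to the reference level.
- Interaction, ±0.5 coding: the treatment coefficient is (b1 + b2)/2.

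**Precision.** Assume that information is proportional to events, that allocation is 2:1 in both strata, and that the true hazard ratio is the same in both. Let f be the share of events in the reference stratum. Relative to the model without interaction:

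- 0/1 coding: SE ratio = 1/√f
- centred coding: SE ratio = ½√(1/f + 1/(1−f)) = 1/(2√(f(1−f)))
- power = Φ((1.96 + 0.84)/ratio − 1.96), starting from an assumed 80% at two-sided 5%

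| f | SE ratio, 0/1 | Power | SE ratio, centred | Power |
|---|---|---|---|---|
| 50% | 1.41 | 51% | 1.00 | 80% |
| 40% | 1.58 | 43% | 1.02 | 78% |
| 30% | 1.83 | 34% | 1.09 | 73% |

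**The same check with event counts.** Take SE = 1/√(D × 2/3 × 1/3), power = Φ(|ln HR|/SE − 1.96), and an assumed hazard ratio of 0.5. With D = 50, SE = 1/√11.11 = 0.300 and power on all events is Φ(0.693/0.300 − 1.96) = 64%. If only the reference stratum's events count, shares of 30%, 50% and 70% give SEs of 0.548, 0.424 and 0.359 and power of 24%, 37% and 49%. Over 30 to 70 events, power is 43–78% on all events and 16–63% on the reference stratum alone.

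**When effects differ by stratum.** In 400 simulated trials (252 subjects, 2:1, equal strata, 28-day placebo risk 32%, true hazard ratios 0.4 under 48 hours and 0.9 at 48 hours or more; median 63 events), the median results were:

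| Model | Treatment HR | SE of log HR |
|---|---|---|
| No interaction | 0.64 | 0.256 |
| Interaction, reference <48 h | 0.40 | 0.403 |
| Interaction, reference ≥48 h | 0.89 | 0.344 |
| Interaction, ±0.5 coding | 0.59 | 0.267 |

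The last value is close to √(0.4 × 0.9) = 0.60, as expected. The centred SE is 0.267/0.256 = 1.04 times that of the simple model. In this example the treatment coefficient gives a hazard ratio anywhere from 0.40 to 0.89, depending on choices that the plan leaves open.

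**The case against.** A reader might infer that the reported hazard ratio will describe one stratum only, with a 41–83% larger standard error. The documents do not support that. It requires 0/1 coding and the raw coefficient reported as the overall effect, and neither is stated. With centred coding the loss is about 4% in the simulation and at most 9% over the shares tabulated. That part of the objection stands, and so does the point that the 80% baseline, the event shares and the hazard ratios are assumptions.

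Nor does the plan say that the interaction model supplies the reported hazard ratio. It could be reported as stratum-specific hazard ratios with a heterogeneity test, which is a legitimate use. That use is not stated either: the text places the interaction inside the model for comparing treatments.

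Section 11.3 could be read as general wording, with 11.4 as the detail, since 11.3 does not exclude an interaction. That is a fair reading, and it makes it too strong to say the protocol knowingly sets two estimands. It does not tell the analyst which model to report.

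Finally, a separate analysis plan is promised. It can settle coding and contrasts, but it cannot follow both descriptions of the model as they stand.

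**Conclusion.** The point holds in limited form and should be corrected. The wording difference is plain on the page: an interaction in Section 11.4 and the synopsis, none named in Section 11.3. It is also certain that a model containing the interaction has no one hazard ratio common to both strata, whatever the coding. How much this matters in practice is not fixed by the documents. It ranges from little (centred coding, or stratum-specific reporting) to a substantial loss of precision and a hazard ratio that applies to one stratum (0/1 coding, raw coefficient reported).

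The reach is confined to Cox results for secondary time-to-event outcomes. The primary endpoint and its analyses, the interim rules, the stratified log-rank test and the sample size are unaffected.

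**What to change.** Use the same statement in Section 11.3, Section 11.4 and the synopsis:

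- The reported hazard ratio and confidence interval come from a Cox model with treatment as the only effect of interest, stratified by (or adjusted for) time since diagnosis in its two randomization levels. The stratified version fits best, because the stratified log-rank test is, apart from ties, its score test; estimate and p-value then address the same comparison.
- The treatment-by-stratum interaction is fitted in a separate model, labelled exploratory, and presented as a heterogeneity test with a hazard ratio and confidence interval for each stratum.

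The cost is about a sentence in each of three places. No planned analysis is lost, no extra data are needed, and the sample size does not change. The separate analysis plan should carry the same wording.

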#### **Number of Subjects to be Enrolled:**

Up to 252 subjects are planned to be enrolled and randomly assigned in a 2:1 ratio to receive RBT-9 or placebo (normal saline).

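### The Day 28 Greenwood test is left undefined, and on its usual reading it is unreliable when deaths are few: it leans towards harm and has less power for benefit than Fisher's test

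*Combined protocol and SAP*

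**What the plan says.** Section 11.4 states: "Time to event outcomes (eg, extubation, hospital discharge, death) will be displayed using a Kaplan-Meier life table", with "treatment distributions compared using a stratified log-rank test and Cox proportional hazards model". It then adds: "A Greenwood test will be performed using the Day 28 estimates from the Kaplan-Meier lifetable". The Efficacy Analysis part of the synopsis carries the same sentence. Section 11.1 lists "Percentage of subjects who are alive at Day 28" among the secondary endpoints.

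Neither place defines the Greenwood statistic. The scale (plain, log or log-log), any stratification, the handling of an arm with no events, the significance level and the precedence relative to the log-rank test are all open. The opening of Section 11 leaves full technical detail to a separate analysis plan, but the combined document contains no such definition.

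On size, the synopsis says: "Up to 252 subjects are planned to be enrolled and randomly assigned in a 2:1 ratio". The table in Section 11.6 gives 84 for "Placebo sample size, n1" and 168 for "RBT sample size, n2". The only level stated for the end of the trial is "2-sided 4.5% Type 1 error remaining at the final analysis".

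**The concern.** A Greenwood variance is estimated within each arm. The hypothesis of interest is that the two arms have the same Day 28 survival, yet the standard error does not use that equality. If an arm has no deaths, its variance is zero and its survival is treated as known to be exactly 100%. Under 2:1 allocation the arm most likely to have no deaths is the smaller one, placebo. The error therefore has a direction: a few deaths on RBT-9 against none on placebo look too convincing, and a few on placebo against none on RBT-9 look too weak.

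At stake is the reading of Day 28 survival, and of other outcomes that may be rare, such as vasopressor or inotrope use. The plan names several analyses of the same outcome and does not say which p-value counts.

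**Working it through.** **Inputs.** From the documents: 84 placebo and 168 RBT-9 subjects, 2:1. Assumed: two-sided 5% (2.5% per tail), because no level is stated for this test; complete follow-up to Day 28; and mortality from 1% to 10%, because no death rate is given.

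**The plan's own figure first.** Section 11.6 states power of 84%, 85% and 84% for the primary endpoint at two-sided 0.045. For 25% versus 10%:
- Pooled rate: (84×0.25 + 168×0.10)/252 = 0.15.
- Null standard error: √[0.15×0.85×(1/84 + 1/168)] = 0.0477.
- Alternative standard error: √[0.25×0.75/84 + 0.10×0.90/168] = 0.0526.
- Power: Φ[(0.15 − 2.005×0.0477)/0.0526] = 84.9%.

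The other two columns give 85.6% and 84.6%. All three agree with the plan to within a point. The plan states no size or power for the Greenwood test.

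**The statistic.** Without censoring, each arm's Greenwood variance is p(1−p)/n, so the plain-scale test is

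z = (pR − pP) / √[pP(1−pP)/84 + pR(1−pR)/168].

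**Two single tables.**
- 0/84 placebo and 4/168 RBT-9 deaths: pR = 0.0238, standard error = √(0.0238×0.9762/168) = 0.01176, z = 2.02, p = 0.043. The pooled-variance score test gives p = 0.154 and Fisher p = 0.304.
- 3/84 placebo and 0/168 RBT-9 deaths: pP = 0.0357, standard error = √(0.0357×0.9643/84) = 0.02025, |z| = 1.76, p = 0.078. The score test gives p = 0.014 and Fisher p = 0.036.

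**Error rates with equal true mortality.** All binomial tables for 84 versus 168 were enumerated and the probabilities of those with |z| > 1.96 added, by direction.

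| Assumed mortality | Expected deaths in 252 | Greenwood, towards harm (nominal 2.5%) | Part left without tables having no placebo deaths | Fisher, towards harm |
|---|---|---|---|---|
| 1% | 2.5 | 3.8% | 0.0% | 0.0% |
| 1.5% | 3.8 | 7.0% | 0.0% | 0.0% |
| 2% | 5.0 | 8.2% | 0.2% | 0.1% |
| 3% | 7.6 | 7.2% | 1.4% | 0.6% |
| 5% | 12.6 | 5.2% | 3.9% | 1.2% |
| 10% | 25.2 | 3.6% | 3.6% | 1.8% |

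The opposite tail, towards benefit, is 0.8% at 2% mortality, 1.1% at 3% and 1.7% at 10%. The two tails together peak near 9%, about 1.8 times 5%, and are 5.4% at 8-10% mortality. In simulations with 10% dropout, the harm tail is 8.0% at 2% mortality and 7.1% at 3%.

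**Power for benefit (placebo versus RBT-9 mortality).**

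| Mortality | Greenwood, plain scale | Fisher | Gap in points |
|---|---|---|---|
| 5% vs 1% | 32.9% | 47.5% | 14.6 |
| 4% vs 1% | 19.8% | 33.4% | 13.6 |
| 6% vs 2% | 25.6% | 34.8% | about 9 |
| 10% vs 3% | 50.4% | 58.5% | 8.1 |
| 10% vs 5% | 23.8% | 28.5% | 4.7 |

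Fisher is a fair comparator because its own false-benefit rate does not exceed 2.5% over 1-15% mortality.

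**Log-log scale.** Here log(−log S) is compared, with variance (1−S)/(n S (log S)²) per arm, and a table with an arm free of deaths counts as no rejection. The harm tail falls to 0.0-0.2% at 2-5% mortality, so the excess goes. Power at 5% versus 1% is 23.9%, lower still. That shortfall belongs to the sparsest settings: at 10% versus 3% the same enumeration gives 59.4%, close to Fisher.

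**The case against.** The strongest reply is that this criticises a statistic the plan does not define. A log-log version has no false-harm excess. At 2% and 3% mortality, 97% and 80% of the excess comes from tables with no placebo deaths, where an analyst might well call the test undefined. The death rate is my assumption, and the patients are hospitalised and at high risk, so 1.5-3% cannot be presumed. The log-rank and Cox analyses are already planned. All of this stands, and it limits the point. It does not remove it: the plan adopts neither safeguard, and the log-log version does not recover the power where deaths are fewest.

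A reader might infer more than the documents support.
- *That the test triples the false-positive rate.* The ratio of about three concerns one tail at 1.5-3% mortality. It is 2.1 at 5% and 1.4 at 10%, and the two-sided ratio is at most about 1.8.
- *That it costs up to 19 points of power.* The 18.8-point gap at 5% versus 1% is against the pooled score test (51.7%). That test is itself liberal for benefit, at 2.7-3.4% for 2-5% mortality. Nor is 18.8 a maximum over all possible rates.
- *That the trial would declare a harmless drug lethal.* No rule uses this test. The stopping and efficacy rules in Sections 9.3.1 and 11.7 rest on conditional power for WHO categories 4 to 8, and Section 11.5 summarises safety descriptively.
- *That a finding on either the Greenwood or the log-rank test would count, roughly doubling the error.* The plan states no such rule; it only leaves precedence open.

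**Conclusion.** The point holds as a weakness in a supplementary secondary analysis. It goes beyond missing detail, because the usual reading of the named test has unequal error in its two directions and lower power for benefit when deaths are few.

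The size depends on the plain scale, separate arm variances, computing the test even when placebo has no deaths, 168 versus 84 subjects, and an assumed mortality. On those terms the worst region is roughly 4 to 8 deaths in the whole trial. By 10% mortality the harm tail has fallen to 3.6%. For common outcomes the matter is small: at 25% versus 10% the Greenwood power is 83.7% against 87.0% for the score test. Rarity has not been shown for extubation or hospital discharge. The primary endpoint and the interim decisions are unaffected. It is worth correcting, but it does not threaten the trial's main conclusion.

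**What to change.** In Section 11.4 and the synopsis:

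1. Remove the Greenwood test as a hypothesis test for death and other rare events.
2. State that the stratified log-rank test already planned governs these outcomes, with an exact or permutation p-value when events are few, and set the event count that triggers it in advance.
3. Report the Day 28 survival difference with a score-based (for example Miettinen-Nurminen) or exact confidence interval.
4. Keep Greenwood variance for descriptive per-arm Kaplan-Meier intervals.

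If the sponsor prefers to keep the test, the minimum is to fix its scale, its rule for an arm with no events and its rank below the log-rank test before any unblinded analysis. That would settle the ambiguity but would not by itself recover power when deaths are few.

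The cost is a sentence or two in two places, with standard software and no change to data collection. The downside is that a sparse split such as 0 versus 4 deaths no longer gives p < 0.05 for harm. The raw counts remain visible to the DSMB, which can judge such a split directly.
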